## 2.0 Background and Rationale

Femoral nerve block catheters have been used to provide analgesia for lower extremity procedures for many years. The catheter is placed near the femoral nerve and a continuous infusion provides a dense nerve block in the distribution of the femoral nerve. This includes blockade of the anterior and posterior divisions supplying the middle cutaneous, medial cutaneous, and muscular (sartorius) branches in the anterior division and the saphenous, muscular (to quadriceps) and articular branches of the posterior division. In particular, the muscular branch supply to the quadriceps makes walking and participating in physical therapy difficult.

A block in the adductor canal can be expected to include the saphenous nerve, vastus medialis, medial femoral cutaneous, articular branches from the obturator and the medial retinacular nerves. This distribution provides the innervation for the medial, anterior and lateral portions of the knee. Van der Wal et al first demonstrated in 1993 the transsartorial approach to blocking the saphenous nerve.(4) In recent years, the ACB has been proposed as a potential successor to the FNB. (1,2,3,5) Kwofie et al investigated quadriceps strength and fall risk in volunteers finding that ACB significantly preserved motor strength and significantly preserved balance. ACB also demonstrated superior analgesia compared to parenteral opioids alone. Further, Kim et al performed a prospective, randomized, controlled trial comparing ACB to FNB with the end point of quadriceps strength, reported analgesia, and opioid intake showing that ACB provided similar analgesia while with less motor block.

This study has been designed to increase the knowledge concerning adductor canal block for total knee arthroplasty surgery as a potentially superior replacement for femoral nerve blocks. Previous studies have well demonstrated the preservation of quadriceps strength and balance. Analgesia also appears to be adequate. This study seeks to replicate those findings with the addition of assessment of physical therapy participation, patient satisfaction, surgeon satisfaction and time to discharge.

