### **4.0 Objectives and Hypothesis**

Following are the specific objectives of this study:

1. Determine the effectiveness of ACB for analgesia compared to FNB as determined by patient reported VAS scores
2. Determine the effectiveness of ACB for analgesia compared to FNB as determined by opioid usage
3. Determine the effectiveness of ACB in physical therapy as determined by early ambulation distance
4. Determine surgeon satisfaction via survey.
5. Determine if there is any difference in time to discharge between the two blocks.

Outline of therapy: Participants in the investigational group will receive an adductor canal nerve catheter prior to TKA surgery. Participants in the control group will receive a femoral nerve catheter prior to TKA surgery. After surgery, the patient will be seen in the recovery room to bolus the catheters and start continuous infusions of ropivacaine. Further details are below in section #

Following are primary endpoints:

1. Pain scores (VAS) at immediate post op, 24 hours, and 48 hours, including highest
2. Opioid consumption at 24 hours and 48 hours pain score at any given time post operatively.
3. Physical therapist assessment of patient participation 0-100.
4. Distance ambulated at 24 hours and 48 hours
5. Patient satisfaction
6. Surgeon satisfaction
7. Hours to discharge.

Study Hypothesis: We hypothesize that the ACB will become the standard of care for TKA analgesia on the basis of improved physical therapy participation and increased patient satisfaction without sacrificing analgesia. With better physical therapy participation, there would be quicker recovery and potentially earlier discharge, increasing patient and surgeon satisfaction.

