## **7.0 Study Interventions and Procedures**

- A. Investigational group participants in the adductor canal block arm will receive an adductor canal block catheter placed under direct ultrasound guidance as follows.
  - a. Patients will be placed supine with their block limb supinated about 20 degrees to facilitate access to the anteromedial thigh. Standard noninvasive monitors will be applied, and oxygen administered via nasal canula. Parenteral midazolam and fentanyl will be titrated to patient comfort.
  - b. Standard skin sterilization, prepping, and draping will be applied to the area. Under ultrasound guidance the needle will be advanced into the adductor canal. After negative aspiration, a bolus of 20 ml 0.5% Ropivacaine will be injected under direct visualization in 5 mL aliquots ensuring proper placement of the needle tip. The catheter will be advanced in this position at least 2 cm and not more than 5 cm and secured to the skin with tegaderm.
  - c. Patients will be evaluated immediately post-operatively in the PACU to determine VAS score from 0-10.

- d. Patients will be given a standard pain regimen while in the hospital. 24 hour opioid consumption will be calculated.
- e. Patients will be evaluated 24 and 48 hours post operatively for VAS score, duration of sensory and motor block, and patient satisfaction from 0-10. The catheter will be removed on post operative day 2.
- f. Patient will be followed up until nerve block resolved.
- g. Physical therapists in the hospital will be surveyed with a standard questionnaire regarding the patients ability to participate in physical therapy sessions on a scale of 0-10. Ambulation distance at 24 and 48 hours will be recorded per their notes.
- h. The surgeons performing the procedures will be surveyed in a general sense regarding their impression of patient recovery with this block
- i. Calculate the hours to discharge for each patient.

B. Control group participants in the femoral nerve block arm will receive a femoral nerve block catheter placed under direct ultrasound guidance with the stimulating needle as follows.

- a. Patients will be placed supine with their block limb exposed to facilitate access to the anterior inguinal area. Standard noninvasive monitors will be applied, and oxygen administered via nasal canula. Parenteral midazolam and fentanyl will be titrated to patient comfort.

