- b. Standard skin sterilization, prepping, and draping will be applied to the area. Under ultrasound guidance the needle will be advanced to the femoral nerve. After negative aspiration, a bolus of 20 ml 0.5% Ropivacaine will be injected under direct visualization in 5 mL aliquots ensuring proper placement of the needle tip. The catheter will be advanced in this position at least 2 cm and not more than 5 cm and secured to the skin with tegaderm.
- c. Patients will be evaluated immediately post-operatively in the PACU to determine VAS score from 0-10.
- d. Patients will be given a standard pain regimen while in the hospital. 24 hour opioid consumption will be calculated.
- e. Patients will be evaluated 24 and 48 hours post operatively for VAS score, duration of sensory and motor block, and patient satisfaction from 0-10. The catheter will be removed on post operative day 2.
- f. Patient will be followed up until nerve block resolved.
- g. Physical therapists in the hospital will be surveyed with a standard questionnaire regarding the patients ability to participate in physical therapy sessions on a scale of 0-100. Ambulation distance at 24 and 48 hours will be recorded per their notes.
- h. The surgeons performing the procedures will be surveyed in a general sense regarding their impression of patient recovery with this block
- i. Calculate the hours to discharge for each patient.

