## 8.0 Statistical Considerations

**General Data Analysis:** All demographic and clinical variables with continuous measures will be expressed as means and standard deviations; categorical factors will be expressed as proportions. For non-normal data, the medians and inter quartile ranges will be displayed. The distribution of the continuous factors will be examined using the Kolmogorov-Smirnov test. For data that are normally distributed, the one-way ANOVA and Student's t-test will be used to compare groups of data. For data that are not normally distributed, the Kruskal-Wallis and Mann-Whitney tests will be used for comparisons. Chi-square and Fisher's exact tests will be used to analyze categorical data. For all comparisons, a value of  $p < 0.05$  will be considered statistically significant.

**Primary Outcome Analysis:** Statistical analyses will be performed using SAS for Windows, version 9.2. Student's t-test will be used to compare post-operative pain scores for investigational and control subjects. Linear regression will be also be used to test the relationship between pain scores and regional anesthetic technique, while controlling for relevant clinical and demographic variables. Distance of first ambulation will be analyzed using Cox proportional hazards model. Student's t-test will be used to compare patient and surgeon satisfaction.

**Statistical Power and Sample Size Estimates:** Sample size (100) was determined using a Cohen's d table assuming a mean pain VAS score of 8 ( $sd = 3$ ) on a scale of 0-10 for control subjects. A sample of 100 participants (50 patients per treatment group) will have approximately 80% power to detect a reduction in pain score of at least 50%, and approximately 99% to detect an 80% reduction in pain score.

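### First-ambulation distance is given a Cox model with no event, axis or censoring rule, and the plan does not reconcile it with the listed 24 h and 48 h distances

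*Combined protocol and SAP*

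**What the plan says.** The Primary Outcome Analysis paragraph of section 8.0 assigns one method to ambulation: "Distance of first ambulation will be analyzed using Cox proportional hazards model".

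Other parts of the document describe ambulation differently:

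- Section 4.0, objective 3: "Determine the effectiveness of ACB in physical therapy as determined by early ambulation distance". The word early is not defined.
- Section 4.0, primary endpoint 4: "Distance ambulated at 24 hours and 48 hours".
- Section 7.0, item g in both arms: "Ambulation distance at 24 and 48 hours will be recorded per their notes".
- Appendix C asks the therapist for the distance covered at the first walking attempt. It does not ask for the time of that attempt.

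The General Data Analysis paragraph of section 8.0 asks for means and standard deviations of continuous variables (medians and interquartile ranges if non-normal). It uses t-tests for normal data and adds: "For data that are not normally distributed, the Kruskal-Wallis and Mann-Whitney tests will be used for comparisons".

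**The concern.** A Cox model needs an event, an axis along which risk accrues, and a rule for observations that end without the event. The plan supplies none of these for first-ambulation distance. The variable that has a named method is not the listed endpoint, and the listed endpoint has only the general default rule.

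Ambulation matters to the trial's rationale. Section 2.0 gives the drawback of femoral nerve block (FNB) as follows: "the muscular branch supply to the quadriceps makes walking and participating in physical therapy difficult". A benefit of adductor canal block (ACB) would therefore be expected to show in walking. If the main output is a hazard ratio, readers will not learn from it how much further ACB patients walked, and may misread its direction. Because no distance is named as the main one, either the first-ambulation result or the 24 h/48 h result could be presented as the ambulation finding.

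**Working it through.** The plan states no hazard ratio, event count, mean distance, SD or power for ambulation, so there is no figure to reproduce. The sample size (50 per group) was set on pain scores. The check is mainly textual, with illustrative arithmetic on assumed distances.

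**1. What the model needs and what the document gives.**

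| Element | Found in the available text |
|---|---|
| Outcome | Distance at first ambulation (section 8.0; collected in Appendix C) |
| Event | Not defined |
| Axis (time or distance) and origin | Not defined |
| Censoring | Not defined |
| Patients who do not walk | No rule |

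The last gap affects any method, not only Cox.

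**2. Was the model meant for another variable?** Section 7.0 records two durations per patient: "Calculate the hours to discharge for each patient" and "duration of sensory and motor block". Neither is assigned the Cox model, and nothing shows that it was meant for them. Time to first ambulation is a possible intention, but the visible forms do not ask for that time.

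**3. What a distance-axis hazard ratio would say.** Take stopping as the event and every distance as observed. Assume exponential distances with means of 80 ft (ACB) and 45 ft (FNB). The hazard is 1/mean, so

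HR (ACB vs FNB) = (1/80) / (1/45) = 45/80 = 0.5625.

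Simulation under the same assumption (3,000 trials, 50 per arm) gave 0.56, with 99.7% of trials below 1. A ratio below 1 here means that ACB patients walked further.

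Now double both means, to 160 and 90 ft. HR = 90/160 = 0.5625, unchanged, while the difference goes from 80 − 45 = 35 ft to 160 − 90 = 70 ft. The Cox partial likelihood uses only the ordering of the distances, so the hazard ratio carries no information in feet.

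**4. Is the test itself sound?** In three assumed null scenarios (2,000 trials each, 50 per arm, all distances as events), the Cox test rejected in 4.6% to 5.6% of trials. The simulation error at 5% is √(0.05 × 0.95 / 2,000) ≈ 0.5 percentage points, so this is consistent with the nominal level. Across six assumed effect scenarios Cox had lower power than Mann-Whitney in five, and power at or above the t-test in five. The ordering depends on the assumed distribution.

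**5. Does the replacement work?** In the same six scenarios, with non-walkers scored 0:

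| Estimate | Coverage of 95% CI | Half-width |
|---|---|---|
| Hodges-Lehmann difference | 96–98% | 14–19 ft |
| Difference in means | 95–96% | 14–31 ft |

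The two can differ: 17 vs 30 ft for lognormal distances (medians 50 vs 30 ft), and 21 vs 35 ft for the exponential case in step 3. One must therefore be named in advance as leading. With 40% zeros in both arms, Hodges-Lehmann coverage rose to about 100%, so that interval is conservative when many patients do not walk.

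**The case against.** The strongest reply is that the plan is under-specified rather than invalid. A Cox model on a distance axis, with each distance counted as an event, is a coherent group comparison, and if every distance is observed no censoring rule is needed. The general summary rule would put mean or median distances beside the hazard ratio; if these are given by arm, size and direction are visible. The 24 h/48 h distances fall under the general test rule, and first-ambulation distance fits objective 3. All of this stands. It does not supply the missing definitions, a between-group difference with an interval, or the choice of main distance. That last gap is part of a wider one: section 4.0 lists seven primary endpoints without ranking them.

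Three stronger readings are tempting but unsupported:

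- *The Cox test inflates type I error or loses power.* The illustrative error rates are nominal, and the power ordering depends on assumed distributions.
- *Two analysts could report hazard ratios in opposite directions for the same benefit.* That requires analysing time to first ambulation, which the visible forms do not collect and which is a different variable from the one named. The realistic risk is misreading the direction of a single ratio.
- *The time of first ambulation is definitely not recorded.* Section 9.0 mentions preprinted data collection sheets that are not shown, so this cannot be established.

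**Conclusion.** The point holds as a mismatch between method, variable and objective. The Cox model is undefined for this outcome in the available text. Even on its most workable reading it yields a ratio that does not measure distance and falls below 1 when patients walk further. The plan specifies no between-group estimate of distance with an interval, and does not reconcile first-ambulation distance with endpoint 4 or say which leads.

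Its numerical consequence cannot be derived from the documents; every distance used above is assumed and serves only to show how the methods behave. Since pain sized the trial and the data needed for a better analysis are already planned, this is a should-fix. The textual conclusion is firm, subject to the forms that are not shown.

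**What to change.** Replace the Cox sentence in section 8.0 with text such as:

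> First-ambulation distance and the distances walked at 24 h and at 48 h will each be compared between groups by Mann-Whitney test. The Hodges-Lehmann difference with its 95% CI is the leading estimate; the difference in means with its 95% CI is supportive.

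Then add three statements.

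1. **Zeros and missing values.** Score 0 only for patients who were assessed and could not walk. Treat discharge before the time point, no therapy session, or missing notes as not assessed, and report the counts by arm. Scoring all of these as 0 would mix inability to walk with early discharge and could penalise the faster-recovering arm.
2. **Main result.** Name one distance as the main ambulation result, consistent with endpoint 4 and objective 3.
3. **If time to first ambulation was intended.** Keep Cox for that endpoint only, define its event, time origin and censoring, and confirm that the time is collected.

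The cost is minor wording and analysis work on data already planned, plus a time field if the third case applies and no form holds it. The drawback is the conservative Hodges-Lehmann interval when many patients score 0, which is a reason to show the difference in means beside it.

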## 1.0 Summary of Study

Peripheral nerve blocks catheters of the femoral nerve have long been used for perioperative analgesia in total knee arthroplasty (TKA). These blocks provide effective analgesia and patient satisfaction for surgical pain relief. However, one of the main drawbacks to the femoral nerve block (FNB) is a denser motor block of the quadriceps muscle that can delay aggressive physical therapy and subsequent recovery from surgery. (1) Recently, there has been increasing interest in performing adductor canal blocks (ACB) with the aim of less motor blockade while providing commensurate analgesia compared to the FNB. (1,2) Current investigative reports have provided only preliminary data, and there is potential to change the standard of care for TKA as more data mounts in favor of ACBs. The goal of this study is to verify the analgesic equivalence of the two blocks, compare patient satisfaction, surgeon satisfaction, and physical therapy grading between the two blocks. Potentially, this would change the standard of care for TKA patients at this institution.

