### **3.0 Significance of Study**

This study has the potential to add to the growing body of evidence that the ACB will eventually be the superior regional anesthetic technique in total knee arthroplasty patients. At this institution, both blocks are currently performed, but the ACB could become the primary technique.

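### The sample-size paragraph states its detectable effect as percentages of an unsourced, untimed control mean of 8; those percentages do not show what 100 patients can detect, and the effect should be given in VAS points

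*Combined protocol and SAP*

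**What the plan says.** The power paragraph of section 8.0 (Statistical Considerations) takes its total of 100 from a table of Cohen's d values, "assuming a mean pain VAS score of 8 ( $sd = 3$ ) on a scale of 0-10 for control subjects". For two groups of 50 it claims "approximately 80% power to detect a reduction in pain score of at least 50"%. Its second claim, for the larger effect, is "approximately 99% to detect an 80% reduction in pain score". It gives no source for the mean or the SD, does not say which pain score they describe, and does not state whether the test is one- or two-sided. The same section sets significance at p below 0.05 and compares pain scores by Student's t-test.

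The control subjects are actively treated. Section 4.0 says "Participants in the control group will receive a femoral nerve catheter prior to TKA surgery", and has the catheter bolused and a ropivacaine infusion started in the recovery room. Section 1.0 says of femoral catheters that "These blocks provide effective analgesia and patient satisfaction for surgical pain relief", and makes analgesic equivalence of the two blocks part of the study's goal. The pain endpoint in section 4.0 covers the immediate post-operative, 24-hour and 48-hour scores and also the highest score.

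**The concern.** An average of 8 on a 0-10 scale is hard to square with a comparator that the protocol presents as effective. It also makes falls of 4 points (50%) and 6.4 points (80%) look available against an active block, in a study whose own expectation is similar analgesia.

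The statistical consequence comes from how the effect is expressed. A percentage of the control mean is a different number of points, and so has different power, at each control mean. If the mean is unsupported, the percentage tells the reader nothing firm about the difference the trial can detect. At stake is what a reader concludes from the sample-size statement, particularly after a non-significant pain comparison.

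**Working it through.** **Inputs from section 8.0:** control mean 8, SD 3, 50 per group, significance level 0.05, two-sample t-test. Two-sided testing is my assumption except where stated.

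**Method.** With D the difference in points, d = D / SD. Power comes from the noncentral t distribution with 98 degrees of freedom and noncentrality d × √(50/2) = 5d.

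**Step 1: the plan's own figures.**
- 50% reduction: D = 0.5 × 8 = 4, d = 4/3 = 1.33, noncentrality 6.67. Power is over 99.99%, against a stated 80%. About 9 per group (normal approximation; 10 with the t distribution) would give 80%.
- 80% reduction: D = 0.8 × 8 = 6.4, d = 6.4/3 = 2.13, noncentrality 10.67. Power is essentially 100%, against a stated 99%.

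The stated powers are not reproduced from mean 8 and SD 3, whether one- or two-sided.

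**Step 2: what does reproduce them.** Taking d = 0.5 and d = 0.8 with 50 per group and one-sided 0.05 gives 79.9% and 99.0%. Two-sided, the same values give 69.7% and 97.7%. At SD 3 they are 1.5 and 2.4 points, which is 19% and 30% of 8. They equal 50% and 80% reductions only if the control mean is 3 (1.5/3 and 2.4/3). It therefore looks as if d values from the table were written as percentages. That is an inference from the numerical match; the document does not say so.

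**Step 3: how the percentage claim moves with the control mean.** The documents give no pain score for femoral-catheter patients, so means below 8, and the SD of 2, are assumptions. Power for a 50% reduction, two-sided 0.05, 50 per group:

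| Control mean | Points | SD 3 | SD 2 |
|---|---|---|---|
| 8 (plan) | 4 | over 99.9% | not needed |
| 5 | 2.5 | 98.5% | over 99.9% |
| 4 | 2 | 91.0% | 99.9% |
| 3 | 1.5 | 69.7% | 96.0% |
| 2 | 1 | 37.9% | 69.7% |

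**Step 4: the figure that does not need the control mean.** The d detectable with 80% power is 0.566, so:
- SD 3: 0.566 × 3 = 1.70 points
- SD 2: 0.566 × 2 = 1.13 points

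At SD 3, 1.70 points is 21% of a mean of 8, 42% of 4, 57% of 3 and 85% of 2.

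**Step 5: where a 50% reduction falls below 80% power.** This happens when half the control mean is less than the detectable difference. The threshold is a mean of 2 × 1.70 = 3.4 at SD 3, or 2 × 1.13 = 2.3 at SD 2.

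**The case against.** The strongest reply is that the documents do not contradict the 8. The only evidence against it is one qualitative sentence about effective analgesia; no numerical score for femoral-block patients appears anywhere. The endpoint list includes the highest score, for which 8 is possible. An immediate score is also listed, and the order of the recovery-room bolus and that score is not stated. This stands. A reader might infer that the control arm will not show a mean of 8, or that the sizing describes the wrong control arm. The documents do not support going that far. They support only that the figure is unsourced, untimed and a poor fit with the comparator as described.

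A second reply is that the loss of power appears only at low assumed means. This also stands: at means of 4 and 5 with SD 3, power for a 50% reduction is 91.0% and 98.5%, above the stated 80%. The 37.9% needs a mean of 2 with the SD still at 3. A reader might infer that the trial is underpowered; these figures do not establish that.

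A third reply is that the mean of 8 did not produce the stated 80% and 99%, and that the detectable difference in points does not depend on it. Both are true. But they are reasons to drop the percentages, not to keep them: the sentence still tells the reader that a 50% reduction from 8 has about 80% power, and it does not. The overlap with the apparent d-to-percentage error is real, and the two should be corrected together.

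**Conclusion.** Wrong as written, in the stated power and effect. From the plan's own mean and SD, a 50% reduction has over 99.9% power rather than 80%. The difference that 50 per group can detect with 80% power is 1.70 points at SD 3, about 21% of 8 rather than 50%. This rests only on the plan's inputs plus a two-sided test, and choosing a one-sided test does not rescue the stated power.

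The further finding, that the percentage has no stable meaning, rests on assumed control means of 2 to 5 and SDs of 2 to 3. Over that range, power for a 50% reduction runs from 37.9% to over 99.9%. Neither a true femoral-block mean nor a shortfall in the sample size of 100 can be established from the documents. The missing source for the 8 is, taken alone, a lack of detail; the error is the effect and power statement built on it.

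**What to change.** Keep the sample size at 100. In section 8.0, delete the 50% and 80% reduction claims. In their place, name the pain score and time point to which the calculation applies, state two-sided alpha 0.05, and give the difference detectable with 80% power and 50 per group: 1.70 VAS points if the SD is 3 and 1.13 if it is 2. No control mean is needed for this.

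If a control mean is kept for context, take it from femoral-catheter knee arthroplasty patients at that time point and cite the source. Section 3.0 notes that "At this institution, both blocks are currently performed", so local records are a natural place to look, but the documents do not say that timed scores exist. Make the change in the same edit that corrects the apparent d-to-percentage conversion.

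The cost is one rewritten paragraph and the loss of the percentage figures; no patients or procedures are added. The change does not supply a margin for the equivalence aim, since a detectable difference is not a demonstration of equivalence.

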## **6.0 Randomization and Recruitment Procedures**

Recruitment: Participants will be recruited, identified, and interviewed by either the study Principal Investigator or one of the co-investigators. The interviewing investigator will confirm eligibility and the absence of any exclusionary criteria. Details of the study (including risks) will be explained to prospective participants to their satisfaction and consent forms will then be signed.

Randomization: Upon enrollment into the study, participants will be randomized 1:1 to either the investigational group (*adductor canal nerve catheter*) or the control group (*femoral nerve catheter*). Randomization will be performed using a random number generator.

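### The stated power does not follow from its inputs: with mean 8, SD 3 and 50 per group, power for a 50% pain reduction is above 99.99%, not 80%; effect sizes of 0.5 and 0.8 appear to have been written as percentages

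*Combined protocol and SAP*

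**What the plan says.** The only justification for the sample size is the power paragraph of section 8.0. It names the method, "Sample size (100) was determined using a Cohen's d table", and the planning values, "assuming a mean pain VAS score of 8 ( $sd = 3$ ) on a scale of 0-10 for control subjects". It then says that 100 participants, 50 in each group, "will have approximately 80% power to detect a reduction in pain score of at least 50%, and approximately 99% to detect an 80% reduction". Section 6.0 confirms equal allocation: "participants will be randomized 1:1 to either the investigational group".

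Elsewhere in section 8.0, pain scores are to be compared by Student's t-test and significance is set at p < 0.05. The plan does not say whether the test is one- or two-sided. The SD of 3 is given for the control group only.

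**The concern.** A 50% fall from a mean of 8 with an SD of 3 is a very large effect, and 50 per group should detect it almost without fail. A claim of only 80% power at that effect suggests that the power came from some other effect size. The pair 50% and 80%, next to a reference to a Cohen's d table, points to d = 0.5 and d = 0.8.

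Two things are at stake:

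- **What the trial can detect.** A reader is told that the trial is sized to find a halving of pain, when it can find a difference of about one fifth. This affects how a null pain result is read, in a trial whose stated aim is to show that analgesia is not lost.
- **A possible shortfall.** If the intended target was d = 0.5 and the test is two-sided, the trial has less power than it claims.

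**Working it through.** **Inputs, all from section 8.0 unless noted.** Control mean 8; SD 3; n = 50 per group (1:1, section 6.0); two-sample t-test; alpha 0.05. Two assumptions are added: the same SD in both arms, and a two-sided test, with one-sided shown alongside.

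**Formula.** d = difference / SD. Power comes from the noncentral t distribution with 2n − 2 = 98 degrees of freedom and noncentrality d × √(n/2) = 5d.

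**1. The plan's figures, taken literally.**

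| Claim | Difference | d | 5d | Stated power | Two-sided power | One-sided power |
|---|---|---|---|---|---|---|
| 50% reduction | 8 × 0.5 = 4.0 | 4/3 = 1.33 | 6.67 | about 80% | 0.999998 | above 0.999999 |
| 80% reduction | 8 × 0.8 = 6.4 | 6.4/3 = 2.13 | 10.67 | about 99% | 1.000 | 1.000 |

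The 80% is not reproduced. The 99% is numerically close to 100% but does not come from these inputs either. For d = 1.33 and a two-sided test, 10 per group gives 80.5% power.

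**2. Could another assumption rescue the 80%?** Power for a 4-point difference, two-sided:

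- Alpha 0.05/7, for the seven primary endpoints listed in section 4.0: 99.99%.
- Worst-case Mann-Whitney efficiency of 0.864 (normal approximation): 99.999%.
- Only 25 per group: 99.6%.
- Largest possible SD. On a 0-10 scale with mean m, the SD cannot exceed √(m(10 − m)). That is √16 = 4.0 at mean 8 and √24 = 4.9 at mean 4. With SDs of 3 and 4.9, the pooled SD is √((9 + 24)/2) = 4.06 and power is 99.8%. With 4.0 and 4.9, the pooled SD is √((16 + 24)/2) = 4.47 and power is 99.3%.
- SD needed for 80%: a common SD of about 7.1, which the scale does not allow.

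**3. The effects read as Cohen's d.**

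| d | Points (d × 3) | Share of 8 | 5d | One-sided power | Two-sided power |
|---|---|---|---|---|---|
| 0.5 | 1.5 | 18.75% | 2.5 | 79.9% | 69.7% |
| 0.8 | 2.4 | 30% | 4.0 | 99.0% | 97.7% |

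Both stated powers are reproduced, but only with a one-sided 5% test. For d = 0.5 and a two-sided test, 80% power needs 64 per group (80.1%; 63 gives 79.5%).

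**4. What 50 per group can detect with SD 3.**

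- Two-sided: 80% power at d = 0.566, which is 1.70 points or 21% of 8; 99% power at d = 0.866, which is 2.60 points or 32% of 8.
- One-sided: 80% power at d = 0.501, which is 1.50 points or 19% of 8.

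**The case against.** The case on the other side accepts the arithmetic and contests what is built on it.

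- **The cause is inferred.** The plan never gives d = 0.5 or 0.8. This stands. The match of both powers and both sets of digits is strong evidence but not proof. The error does not depend on the explanation.
- **The shortfall is conditional.** The plan states no sidedness, and with a one-sided test 50 per group does give 80% power at d = 0.5. This also stands: the 70% figure applies only if d = 0.5 was the target and the test is two-sided.
- **The 99% claim is not materially wrong.** True, since 99% and 100% barely differ. The 80% claim carries the point.
- **The error is harmless because it understates power.** This holds only for the literal reading. On the d = 0.5 reading with a two-sided test, the plan overstates power by 10 percentage points.
- **Restating the detectable difference works backwards from the sample size.** This is a fair caution. The sponsor should confirm that the restated difference is one it wants to detect.
- **A power statement for a pain reduction does not support the equivalence aim in section 1.0.** That is a separate matter, and correcting this sentence does not settle it.

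**Conclusion.** The concern holds. On the plan's own inputs, power for a 50% reduction is above 99.99% two-sided, not about 80%. The equal-SD assumption does not drive this: with the largest SDs the scale allows in both arms, power is still 99.3%. No other part of the document corrects the sentence.

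The difference that 50 per group can detect with 80% power is 1.70 points two-sided (21% of the control mean) or 1.50 points one-sided (19%). The plan's 4 points is more than twice either figure (4/1.70 = 2.4; 4/1.50 = 2.7). These detectable differences assume SD 3 in both arms and full data on all 100 patients.

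The point must be fixed, because this sentence is the trial's only sample-size justification. Taken literally, it would justify about 20 patients in total rather than 100.

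**What to change.** Keep N = 100, remove the 50% and 80% reduction claims, and replace the sentence with wording such as:

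> With an SD of 3 in each arm and 50 patients per group, a two-sided 5% t-test has 80% power to detect a difference of 1.7 points in mean VAS (d = 0.57, 21% of a control mean of 8) and 99% power to detect 2.6 points (d = 0.87, 32%).

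The sponsor should confirm that 1.7 points is an acceptable target. If so, the cost is one sentence of protocol text and no extra patients. If d = 0.5 (1.5 points) was intended, the plan should do one of three things: acknowledge about 70% power two-sided, justify and state a one-sided 5% test (about 80% power), or enrol 64 per group (128 in total, 28 more).
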